14.2. SAMPLE SIZE

Sample size and power calculations are based on a non-inferiority hypothesis for the primary outcome measure. Secondary outcome measures are not powered. The statistical design is based on a distribution-based method informed by data from the previous trial (16), clinical co-applicant experience and consensus, reported recommendations of minimally important differences in knee disease and feedback from the PPI focus group. A median 12-point credible minimal difference (range 4 to 20) for patient reported KOOS pain has been recommended (19) and 13-points for patients with knee OA (42). This is supported by patients who report they would accept a 10-15% (translated to 10-15 points) increase in pain to retain their knee. Based on this consensus for a minimally important difference, the non-inferiority threshold is defined to be at least 33% less at a threshold of 8. Previous observational studies of KOOS pain have reported variability (SD) from 15 to 21 (3,43–45).

A one-sided significance of 2.5% is used which allows two-sided 95% confidence intervals to be presented. The target recruitment is based on demonstrating non-inferiority within a limit of 8 points. Ignoring drop-out within 12-months, 146 patients recruited to each group would have 90% power to demonstrate non-inferiority within a threshold of 8 points and variability assumed SD=21. Allowing for 15% dropout, the target is inflated to 172 patients in each group resulting in an overall recruitment target of 344 patients. The underlying assumptions of the statistical design will be monitored by the DMEC.

No sample size adjustment has been made to accommodate surgeon learning curve since external fixation is a common procedure which orthopaedic surgeons are frequently required to do for trauma.

15. ECONOMIC EVALUATION

A within trial cost-effectiveness analysis within 24-months will be conducted adopting the perspective of the NHS and Personal Social Services. Costs and outcomes occurring beyond 12 months will be discounted at 3.5%. The primary outcome is Quality Adjusted Life Years (QALYs). The proposed methods for the economic evaluation follow the NICE reference case (46).

Health utility values will be estimated through administration of the EQ-5D-3L. Unit costs for health service resources will be obtained from national sources (e.g. Personal Social Services Research Unit [PSSRU] and NHS Reference Cost). The intervention cost will include theatre time, knee components used during the primary admission and during any knee-related readmissions or revisions.

The differences in mean costs and effects will be presented using incremental cost effectiveness ratio (ICER). Net incremental monetary benefit (NMB) will also be computed. The level of sampling uncertainty around the ICER will be determined using a nonparametric bootstrap to generate 10,000 estimates of incremental costs and effects. Bootstrapped estimates will be plotted on the cost-effectiveness plane to illustrate the uncertainty surrounding cost-effectiveness estimates (47). Bootstrapped estimates of cost and effects will also be used to compute the probability that each intervention is cost-effective for a range of cost-effectiveness thresholds. The results will be presented as cost-effectiveness acceptability curves (CEAC) (48).

In order to assess the long-term cost-effectiveness of KJD compared to KR, a decision analytic cost-effectiveness model will be used to estimate the likely impact on costs and benefits over 20 years. The model will be constructed and described in line with best practice (46). Data to populate the model will be derived from three sources:

1. The literature

2. Ongoing follow-up studies and clinical trials of Knee Joint Distraction as coordinated by UMC Utrecht (currently N=174 patients in follow-up with max 10 year follow-up, 105 started end 2017)

3. Publicly available UK orthopaedic registry data which will provide transition probabilities on knee replacement initial effects and longer-term effects.

Parameter uncertainty will be addressed using probabilistic sensitivity analysis. The distribution of expected costs and effects will be provided and the probability that the intervention is cost-effective given a range of willingness to pay thresholds will be represented via CEACs.

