10.3.1. Knee joint distraction

A definitive external fixator construct should be used which allows for controlled linear distraction across the knee joint of 5mm along the mechanical axis of the limb. The exact nature of the construct will depend on the equipment available at the site and surgeon preference. A list of permitted devices will be detailed in the surgical manual, and sites wishing to use devices not appearing on this list must provide CTRU with details of their preferred construct during site feasibility for prior approval. All equipment used must be CE-marked and intended to be used for distraction.

During surgery, the external fixation frame should be assembled according to this manual, with a focus on meticulous pin insertion to minimise the risk of complications. Fluoroscopy will be used to assist correct pin placement. Once the assembly is complete, 2mm of axial distraction (measured at frame) should be applied across the knee joint.

The limb should then be cleaned and a final check made for soft tissue tension around fixation elements with further skin releases made as required. Pin-sites should be dressed with an absorbent non-shedding dressing. Clips and bungs are available with various systems to keep these in place and apply gentle pressure.

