10.4.3. Fixator removal (KJD arm only)

External fixators will be removed under general or regional anaesthesia at Week 6 after placement, as detailed in the surgical manual. Standardised AP and lateral x-rays will be taken before the frame is removed, as detailed in the radiography manual.

Participants will be admitted as day case patients with appropriate preparation for anaesthesia according to local protocols. Following administration of anaesthesia, all dressings will be removed. The external fixator assembly will be removed leaving the pins in place. The pin-sites will be cleaned thoroughly and the pins will then be removed by hand. Pin-sites must be left open and covered with adhesive dressings.

A gentle manipulation under anaesthesia (MUA) to achieve at least 0 to 90 degrees of motion should then be attempted. Once recovered from anaesthesia the participant will be allowed home, usually the same day.

Pin-sites will be kept covered until they have healed and immersion in water avoided. Participants are generally permitted to shower as long as the pin-sites are covered.

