This trial-specific questionnaire will measure participant's reported health care use, days off work and private costs due to knee OA using a bespoke short self-reported schedule adapted from forms already developed at the University of Leeds. Healthcare use includes the number of contacts with clinical staff (occupational health, primary care staff, rheumatologists etc.) and medications as a result of knee OA.

6. Implementation processes and intervention fidelity

Quantitative

Treatment fidelity will be assessed on the surgical CRF which will record whether the mandatory components of surgery were performed as detailed in the surgical manual and any deviations explained.

Post-operative x-rays (AP and lateral) will also be returned and assessed by central review.

Qualitative

Outcomes relating to the qualitative evaluation with surgical and clinical staff of intervention processes and qualitative fidelity are described fully in Section 16.

7. Qualitative evaluation of participant experiences

Outcomes relating to the qualitative evaluation of participant experiences are described fully in Section 16.

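### The patient resource-use form covers only care attributed to knee OA, so care arising from the operation, notably routine pin-site care after KJD, could be missed; Section 15 also leaves the fixator unnamed

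*Protocol*

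**What the plan says.** Section 15 plans a within-trial cost-effectiveness analysis over 24 months, "adopting the perspective of the NHS and Personal Social Services", and says its methods follow the NICE reference case. On the cost of the intervention it states: "The intervention cost will include theatre time, knee components used during the primary admission and during any knee-related readmissions or revisions".

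Section 11.2 (item 5) describes the patient questionnaire that supplies resource use. It is a bespoke, trial-specific form covering "reported health care use, days off work and private costs due to knee OA". Health-care use is described as contacts with clinical staff "and medications as a result of knee OA". The staff examples include primary care and the list is left open. Nursing, dressings and care following the operation are not mentioned.

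The KJD pathway has elements that KR does not:

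- **Device.** Section 10.3.1 specifies an external fixator: "The exact nature of the construct will depend on the equipment available at the site and surgeon preference".
- **Second procedure.** Section 10.4.3 states: "External fixators will be removed under general or regional anaesthesia at Week 6 after placement", and "Participants will be admitted as day case patients with appropriate preparation for anaesthesia according to local protocols".
- **Aftercare.** Sections 10.3.1 and 10.4.3 describe dressing the pin sites at surgery and keeping them covered after removal until they heal.

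**The concern.** Cost-effectiveness is part of the trial's stated aim (Section 6). An incremental cost is fair only if resources in both arms are captured on the same footing. Here the form attributes use to the disease, whereas some of the care that differs between the arms comes from the operation. A participant who sees a practice nurse about healthy pin sites has had care because of the frame, and may reasonably not count it as care for osteoarthritis.

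Unit costs and modelling choices can be settled later. The questions put to participants cannot: a contact not asked about at the time is lost to the analysis. What is at stake is the KJD minus KR cost difference, and with it the within-trial ICER, net monetary benefit and acceptability curves. The primary outcome is not affected.

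**Working it through.** The protocol gives no cost figure for this point, so there is none to reproduce. The check is whether each KJD-only item has a source, and then what an omission would do.

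**Step 1. Sources by item** (Sections 10.3.1, 10.4.3, 11.2, 12.2, 13.1, 13.2.2 and 15)

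| Item | Named in Section 15? | Source other than the patient form | Recoverable? |
|---|---|---|---|
| Theatre time, fixator placement | Yes | Surgical details, day of surgery | Yes |
| External fixator and pins | No | Allocation; device from a permitted list or approved in advance | Yes |
| Week-6 removal admission | Only if it counts as a knee-related readmission | Surgical details at week 6 | Largely |
| Pin-site infection, antibiotics | No | Infection recorded with antibiotic use; complication CRFs; concomitant medications | Largely |
| Routine pin-site care, no complication | No | None evident | Only if the form elicits it |

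The last row is the real gap. Section 13.1 defines a complication as an untoward medical event, and uneventful pin-site care is not one. No complication CRF would therefore record it.

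**Step 2. Timing.** Section 12.2 schedules the resource-use form at baseline and at months 3, 6, 12 and 24; on the day of surgery only the KOOS is completed. The frame comes off at week 6, and no form is scheduled then. Taking three months as about 13 weeks, the month 3 window of plus or minus 4 weeks runs from 13 − 4 = 9 to 13 + 4 = 17 weeks after surgery, or 3 to 11 weeks after removal. The frame-wearing period therefore rests on one later form worded around osteoarthritis.

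**Step 3. Direction.** Let c_J and c_R be the missed cost per patient in the KJD and KR arms.

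- Recorded incremental cost = true incremental cost − (c_J − c_R).
- Recorded net monetary benefit = true value + (c_J − c_R).

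For a KJD-only item of cost F, c_J = F and c_R = 0, so incremental cost is understated by exactly F and KJD is favoured. For the form as a whole c_R need not be zero, because wound care and other aftercare for KR are also due to the operation. The sign then depends on whether c_J exceeds c_R, and if they are equal the bias is nil.

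**Step 4. Scale, on assumed values only.** A net omission of F equals F ÷ threshold in QALYs. Section 5.1 cites a willingness to pay of €20,000 per QALY from an earlier evaluation; using 20,000 purely as a conversion rate:

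- 500 ÷ 20,000 = 0.025
- 1,000 ÷ 20,000 = 0.05
- 2,000 ÷ 20,000 = 0.10
- 4,000 ÷ 20,000 = 0.20

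These costs are assumptions. They show how an omission would carry through and do not estimate what would be missed.

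**The case against.** A reader might infer that the fixator and all care specific to KJD are excluded from the costing, so that KJD is bound to look cheaper than it is. The documents do not support that:

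- Section 15 says what the cost will include and does not close the list. The NHS and Personal Social Services perspective covers the fixator, the removal admission and NHS pin-site care in principle.
- Every participant treated with KJD receives a fixator, so an analyst would be expected to cost it. Removal, infections, antibiotics and additional knee surgery all have site-reported sources.
- Operation-related care could be missed in both arms, so the net direction for the form is not certain.

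Three further objections have some force. The questionnaire is not shown; Section 11.2 only summarises it, and the actual items may be broader. Participants may count care after surgery for osteoarthritis as care due to osteoarthritis. And the protocol does not say that nurses provide the pin-site care.

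What remains is narrower. The summary states an attribution rule and is not merely silent. Whether pin-site contacts are captured would depend on how each participant reads that rule. Detailed costing can be left to a later analysis plan, but such a plan cannot restore answers to questions that were not asked.

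**Conclusion.** The point holds in a limited form. As described, the form could miss care arising from the operation, notably routine, uncomplicated pin-site care, which exists only with KJD and has no other evident source. That loss could not be made good at analysis. The wording of Section 15 is lopsided, naming the KR device and not the fixator, but this is a matter of clarity because the items can be costed from data already planned.

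Any omitted KJD-only cost favours KJD by its full amount. For the form overall, bias towards KJD is likely rather than proven, since KR aftercare may be missed too. The size cannot be derived from the protocol. The conclusion assumes that the questionnaire items follow the Section 11.2 summary and that some routine pin-site care involves NHS contacts. It bears on the economic evaluation only.

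**What to change.** 1. **Resource-use form and Section 11.2.** Ask in both arms about care related to the knee, the knee operation or its complications. Make wound or pin-site care by practice or community nurses a named item. Keep the existing time points.
2. **Section 15.** State that the intervention cost covers devices and consumables in both arms (implant, external fixator and pins) and every planned trial procedure, including the week-6 removal admission. The week-6 surgical details can supply the removal data.

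The cost is a slightly longer form and a change of wording in two sections, with no new visits and no change to clinical care. KJD may come out with a less favourable cost. The form should be changed before participants complete it after surgery, because the lost information cannot be collected later.

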3. TRIAL SUMMARY

Trial Title	K nee AR throplasty versus joint D istraction S tudy for osteoarthritis						
Trial Acronym	KARDS						
Trial Design	Multi-centre, pragmatic, open-label, two-arm individually randomised controlled non-inferiority trial.						
Trial Aim	To investigate the clinical and cost-effectiveness of Knee Joint Distraction (KJD) compared to Knee Replacement (KR).						
Trial Objectives To examine the clinical effectiveness of KJD compares based on patient reported pain 12 months after surges Secondary objectives To examine and report:							
	 Patient reported outcomes and quality of life within 24 months after surgery Objective assessment of knee function Rates of complications, including infection The need for further intervention within 24 months after surgery KJD's potential as a cartilage regenerative therapy Estimate of short and long term cost-effectiveness Implementation processes and intervention fidelity Participant experiences of the trial/interventions and possible facilitators or barriers to wider implementation 						
Trial Population:	People aged between 18 and 65 with symptomatic knee osteoarthritis, severe enough to warrant unicompartmental or total KR, with intact collateral ligaments and alignment not requiring correction.						

Randomisation:	344 patients will be randomised on a 1:1 allocation ratio to KJD (intervention arm) or KR (control arm) based on a minimisation algorithm with random component stratified by delivery unit and osteoarthritis severity.					
Trial Interventions:	KJD: Knee joint distracted by 5mm for six weeks using an external fixation frame KR: unicompartmental or total knee replacement					
Trial Duration:	All participants will be followed up for 24 months after surgery.					
Outcome measures:	 Primary outcome measure KOOS pain score within 12-months from surgery. Secondary outcome measures Patient reported outcomes and quality of life outcomes Objective assessment of knee function Incidence of complications Joint space width 					
	 Cost-effectiveness Implementation processes and intervention fidelity Qualitative evaluation of participant experiences 					

FLOW DIAGRAM 3.1.

Screening (outpatient knee clinic)

Potentially eligible patients identified from knee outpatient clinic lists: eligibility confirmed in clinic and eligible patients informed about the trial and given participant information sheet.

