The number of young patients undergoing KR is increasing year on year (7). The risk of failure of KR is disproportionately higher in the young and active. The age adjusted estimates of lifetime risk of revision after KR is 35% in males between 50-54 years of age. These estimates continue to be at least 2 times higher for men and women aged 65 or under as compared to those older than 70 years (7). With improved life expectancy, many of these young patients with KR are likely to spend many more years than previously expected with a revision implant, which are associated with poor outcomes and high costs (7). The risk of re-revision in these cases is significantly higher, and associated morbidity (infection, cardio-respiratory problems, stroke, venous thrombo-embolism) and mortality increases with every subsequent surgical intervention.

KARDS protocol v1.0_190927

The decision to have surgery is largely based on a balance between potential risks and benefits. The James Lind Alliance Priority Setting Partnership (8), a public–patient involvement (PPI) group, has established that the relation between timing of joint replacement and best outcome is one of the most significant concerns for patients with OA. This is of particular importance in determining optimum timing for surgery in patients who are expected to outlive their primary KR. Therefore, the length of time a KR will last (before requiring revision) becomes a major factor in deciding whether to proceed with KR surgery.

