The age at which a patient receives a KR is the most important factor affecting both implant survival as well as clinical outcomes, with patients younger than 60 years having the worst clinical outcomes and the highest revision rate (5,7). A combined endpoint analysis including revision, poor function and significant pain has shown the KR success to be as low as 59% at 12 year follow-up in patients younger than 60 years (9). Currently 40% of primary KRs and up to 44% of KR revisions in Europe are performed in patients aged ≤65 years (10). Life expectancy of a 65-70 year old in the UK today is typically projected to be an additional 18 (men) to 21 years (women) (11) and thus will need a well-functioning KR for those many years if performed at the age of 65. The risk of revision KR is <5% if the first KR is performed at around the age of 70 years. A procedure which will delay the KR at least up to the age of 70 is therefore worth considering, provided it does not hamper the ability to undergo a KR at a later stage. There is an increasing and unmet need for alternative treatments for knee OA which will delay or reduce the need for KR.

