5.1. RATIONALE FOR THE TRIAL

There is a clear unmet need for a treatment which postpones the time to first KR in the young population (≤65 years) with knee OA, thereby preventing or postponing revision KR (9,10). To bridge this gap in treatment options, there is a need for cost-effective strategies that preserve the joint. Knee joint distraction (KJD) is one such treatment option to address the current problems associated with KR in the younger population. KJD is a joint sparing technique not currently widely used in the UK but has shown good mid-term outcomes in studies conducted in the Netherlands (12–14). It utilises the well-established orthopaedic practice of external fixators for fracture stabilisation, except that the stabilisation is across a synovial joint. KJD harnesses intrinsic joint

repair potential, providing cartilage repair and normalisation of subchondral bone abnormalities (12).

KJD aims at mechanically unloading the damaged tibiofemoral joint surfaces of the OA knee and allowing 6 weeks of biomechanical joint homeostasis by distracting the femur from the tibia by approximately 5 mm. This distraction is achieved and maintained using an external fixator assembly. The mechanical unloading prevents further wear and tear of the articular surfaces and also provides a temporary biomechanical and biochemical environment enabling tissue repair (14). Typical external fixators consist of distraction tubes outside of the leg which are attached to bone pins that are surgically inserted into the femur and tibia and are aligned along to the mechanical axis of the leg, bridging the knee. Bone-pins are positioned extraarticular; outside the area that is involved in primary TKR. This precaution is important to prevent potential infection because of previous KJD treatment. This procedure can be performed in 30-45 minutes. To date, none of the patients receiving TKR after KJD treatment (16.6% at 5 years) suffered from a joint or deep wound infection (personal communication).

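### The 20-year horizon of the long-term cost-effectiveness model is given without a reason and is shorter than remaining life for most participants, materially so for those who enter at about 55 or younger

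*Protocol*

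**What the plan says.** Protocol Section 15 describes two economic analyses: a within-trial analysis to 24 months, and a model for the longer term. On the second it states: "In order to assess the long-term cost-effectiveness of KJD compared to KR, a decision analytic cost-effectiveness model will be used". The horizon is set at the end of that sentence, where the model's stated task is to "estimate the likely impact on costs and benefits over 20 years". No reason is given for the 20 years. The sensitivity analysis planned for the model is probabilistic and addresses parameter uncertainty. One of the three data sources is a set of KJD cohorts with follow-up of at most 10 years.

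Three other parts of the protocol bear on the horizon:

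- **Population.** Section 3 defines it as "People aged between 18 and 65 with symptomatic knee osteoarthritis".
- **Life expectancy.** Section 5 states: "Life expectancy of a 65-70 year old in the UK today is typically projected to be an additional 18 (men) to 21 years (women".
- **Rationale.** It is framed over a lifetime. Section 5 says "The age adjusted estimates of lifetime risk of revision after KR is 35% in males between 50-54 years of age", puts the revision risk below 5% when the first KR is done at around 70, and concludes: "A procedure which will delay the KR at least up to the age of 70 is therefore worth considering". Section 5.1 describes the need for a "treatment which postpones the time to first KR in the young population", so as to prevent or postpone revision.

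Section 6.2 lists short- and long-term cost-effectiveness as a secondary objective.

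**The concern.** The argument for KJD is that a younger patient who keeps the knee for some years has the first KR later and faces less revision surgery over the rest of life. A model meant to show whether this is worth the cost should run long enough to count those consequences. With entrants aged 18 to 65, and 18 to 21 years still expected at the upper age limit, a 20-year window closes before expected death for many of them.

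The horizon is a structural choice, so the planned probabilistic analysis cannot show how much the result depends on it. The reader would get one long-term figure with no indication of what happens after year 20 in the younger patients for whom the treatment is chiefly intended.

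**Working it through.** The protocol gives no derivation of the 20 years, so there is no figure to reproduce. The check compares the horizon with the protocol's other figures.

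**Inputs.** Horizon 20 years (Section 15). Age at entry 18 to 65 (Section 3). Remaining life 18 years for men and 21 for women (Section 5, given for age 65-70 and taken here at 65). Discount rate 3.5% (Section 15, where it is stated for the within-trial analysis; its use in the model is an assumption). KR after KJD 16.6% at 5 years (Section 5.1).

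**1. Remaining life and share covered.** For entry at age *a*, remaining life is T = (65 − a) + 18 for men or + 21 for women. This ignores deaths before 65. The undiscounted share covered is 20/T. The discounted share is (1 − 1.035^−20) / (1 − 1.035^−T), with numerator 1 − 0.503 = 0.497.

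| Age at entry | T (men / women) | 20/T | Discounted share |
|---|---|---|---|
| 60 | 23 / 26 | 87% / 77% | 91% / 84% |
| 55 | 28 / 31 | 71% / 65% | 80% / 76% |
| 50 | 33 / 36 | 61% / 56% | 73% / 70% |
| 45 | 38 / 41 | 53% / 49% | 68% / 66% |

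For example, at 55 for men: 0.497 / (1 − 1.035^−28) = 0.497 / 0.618 = 0.80.

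**2. Allowing for deaths before 65.** With an assumed 1% yearly mortality before 65, T falls to 25.8 / 28.5 years at 55 and 29.4 / 32.0 at 50. The same formula then gives about 85% / 80% covered at 55 and 78% / 75% at 50. The gap shrinks but remains. Both steps treat remaining life as a fixed term. The spread of lifetimes is not modelled, so the shares are approximate.

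**3. Who is not cut short.** T ≤ 20 requires a ≥ 63 for men. For women it requires a ≥ 66, which is outside the age limit, although at 65 the shortfall is only one year. The protocol gives no age distribution. If half are men and ages are uniform over 18-65, 40-65, 50-65 or 60-65 (assumptions), about 3%, 6%, 9% or 25% are fully covered. That leaves 75% to 97% with a horizon shorter than expected life.

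**4. Horizon against the age-70 goal.** Age 70 is reached 70 − a years after surgery, which leaves a − 50 years of horizon: 15 years for entry at 65, 10 at 60, 5 at 55 and none at 50. Only entrants at 50 or younger have no modelled time after age 70.

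**5. How much KR after KJD falls inside the window.** A constant hazard fitted to 16.6% at 5 years is −ln(1 − 0.166)/5 = 0.0363 per year. This gives 30% with KR by year 10, 52% by year 20 and a median of 19.1 years. Weibull shapes from 0.75 to 2 (assumptions) give 40% to 95% by year 20 and medians of 30 to 10 years. So a large part of the KR after KJD is counted. Between about 5% and 60% of KJD knees would reach year 20 without KR, and any later KR or revision in them would be uncounted.

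**The case against.** The strongest objection is that the protocol already places substantial benefit inside 20 years. Section 5.1 cites a prediction that KJD saves over 100 total KRs and about 30 revisions over 20 years in patients under 55, the group most affected by the truncation. Section 5 also reports KR success as low as 59% at 12 years in patients under 60, so much failure in the KR arm falls well inside the window. A reader might infer that the main long-term effect of KJD is cut off. The documents do not support that: the delay of first KR lies largely within 20 years, and what is lost is part of the later effect.

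A reader might also infer that the model stops about when the deferred KR would occur. On the age-70 goal this fits only entry at about 50 or younger, and age 70 is an aim, not a predicted date.

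The horizon also involves a trade-off. KJD data reach at most 10 years, so 20 years already doubles the evidence, and a lifetime run from age 50 (33 to 36 years) stretches it more than threefold. Twenty years matches the earlier prediction and allows comparison with it. Scenario detail can reasonably wait for a later analysis plan.

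These arguments support keeping the 20-year result. They do not explain why it should be the only one. Savings within 20 years do not show that the window is sufficient, since a KR done in year 21 counts as one avoided.

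**Conclusion.** The point holds as a modest improvement to a secondary analysis. The horizon is unexplained and shorter than expected remaining life for most participants. The shortfall is slight near 60 (9-16% of discounted life-years left out) and material around 55 (20-24%) and 50 (27-30%). With an assumed 1% yearly mortality before 65, the last two become about 15-20% and 22-25%. All of this rests on reading the 18 to 21 years as applying at 65, on a 3.5% rate in the model, and on treating remaining life as a fixed term.

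Two further inferences go beyond the documents. The first is that nearly all participants are cut short: the age mix is not given, and men aged about 63 to 65 are covered to their expected life span. The second is that the truncation works against KJD or would change the sign of the result. Stopping at year 20 drops late revisions in the KR arm, which disfavours KJD, and drops late KRs and their revisions in the KJD arm, which favours it. The net direction is unknown, and no incremental cost or QALY calculation shows a change of sign. What the cited reference case says about time horizon is not in the document and is not relied on here.

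**What to change.** In Section 15, keep the 20-year result for comparability and give the reason for that length. Add a lifetime-horizon run of the same model, reported beside it and by age band at surgery. Add scenario analyses for how KJD survival is extrapolated beyond the 10 years of cohort data, so that the reader can see how far the lifetime result depends on them.

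The cost is one further model run and a few lines of text. The downside is more reliance on extrapolation, which the scenarios make visible. Data collection, the primary analysis and the sample size do not change.
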